8.2.2 Exclusion Criteria

None of the following exclusion criteria shall be met at Screening Visit and will be re-checked at Day 1 Cycle 1:

1. Previous treatment with a PI3K inhibitor.
2. Hypersensitivity and/or contraindication to MEN1611, cetuximab or to any component of the formulations.
3. Inability to swallow oral medications.
4. Brain metastases, with the exception of patients with previously treated brain metastases (including radiation and/or surgery) > 4 weeks before the Screening Visit and only if clinically stable (as determined by the Investigator), and not receiving corticosteroids.
5. NCI CTCAE v5.0 Grade ≥ 2 diarrhoea, which is not resolved in the week prior to the start of the study treatment (Day 1 of Cycle 1).
6. History of significant, uncontrolled or active cardiovascular disease, specifically including, but not restricted to:
 - a) Myocardial infarction within 6 months prior to the first dose of any study treatment (Day 1 of Cycle 1,).
 - b) Acute coronary syndromes (including unstable angina, coronary artery bypass grafting [CABG], coronary angioplasty or stenting) within 6 months prior to first dose of any study treatment (Day 1 of Cycle 1,).
 - c) Congestive heart failure (CHF) New York Heart Association Class III-IV.
 - d) Clinically significant atrial arrhythmia (including clinically significant bradyarrhythmia), as determined by the Investigator.
 - e) Long QT syndrome or other risk factors for “Torsades de Pointes” or increased QTc interval according to Fridericia formula (QTcF > 450 msec for males and QTcF > 460 msec for females).

f) Ventricular arrhythmia.

7. Symptomatic thromboembolic events or cerebrovascular accident including transient ischaemic attack within 6 months prior to the start of any study treatment (Day 1 of Cycle 1).
8. Uncontrolled hypertension (defined as persistent BP of $\geq 150/90$ mmHg despite treatment, measured on at least 2 separate occasions).
9. Known active or uncontrolled pulmonary dysfunction.
10. Any serious and/or unstable pre-existing psychiatric or neurologic illness or other conditions that could interfere with patient's safety.
11. Uncontrolled diabetes mellitus (HbA1c $> 7\%$) and FPG > 126 mg/dL.
12. Known history of human immunodeficiency virus (HIV) infection or active infection with hepatitis C virus (HCV) or hepatitis B virus (HBV).
13. Patients diagnosed with another primary malignancy, except for: adequately treated non-melanoma skin cancer or cervical cancer in situ; or patients with another primary malignancy who are definitively relapse-free for at least 3 years since the diagnosis of the other primary malignancy.
14. Concurrent chronic immunosuppressive treatment either with steroids or other immunosuppressive agents.
15. Any chemotherapy, radiotherapy, immunotherapy, major surgery, biologic therapy or any other investigational agent within 28 days of the first administration of the study treatment or within five times the half-life of the investigational agent, whichever is longer.
Note: Patients may receive palliative radiotherapy for painful bone metastases, as long as $\leq 25\%$ of the bone marrow was irradiated and does not affect target and non-target lesions being assessed. (Please see section 8.4.8.)
16. Any other concurrent severe and/or uncontrolled concomitant medical conditions (e.g. active or uncontrolled infection) that could cause unacceptable safety risks or compromise compliance with the protocol.
17. [REDACTED]
18. Pregnant or breastfeeding women.
19. Inability or unwillingness to abide by the study protocol; legal incapacity or limited legal capacity.
20. Warfarin sodium therapy or any other coumadin-derivative anticoagulant.

8.2.3 Withdrawal of Patients from the Study or Discontinuation of the Study Treatment

Participation in the study is strictly voluntary and patients have the right to withdraw from the study at any time without explanation. This will not affect their rights for future medical care. Patients may also be discontinued from the study treatment at the Investigator's discretion or at specific Sponsor's request at any time.

8.2.3.1 Withdrawal from the Study

The reasons for protocol-specified patient withdrawal are listed below:

- Informed consent withdrawn or the patient requests discontinuation from the study.
- Any medical condition or personal circumstance which, in the opinion of the Investigator or the Sponsor, exposes the patient to risk by continuing in the study or does not allow the patient to adhere to the requirements of the protocol.
- Death.

8.2.3.2 Withdrawal from the Study Treatment

Patients will be withdrawn from the study treatment if they experience:

- Any protocol deviation which in the opinion of the Investigator or the Sponsor exposes the patient to risk by continuing the treatment.
- Any medical condition or personal circumstance or AE with a possible, probable or certain drug-causality as per Investigator's judgement which exposes the patient to risk by continuing the treatment.
- Disease progression.
- Delay in scheduled treatment exceeding 21 days due to study drug related toxicity.
- Occurrence of pregnancy.
- Patient's request.

All patients shall undergo the End of Study Visit at the time of study withdrawal or discontinuation of the study treatment. Unscheduled assessments showing disease progression and leading to patient's withdrawal can replace the End of Study Visit provided that all assessments/procedures scheduled for this visit are completed.

If a patient prematurely terminates the study as per patient's request, data already collected will be used and analysed for the purpose of the study, as per local regulation.

In case of withdrawal of consent, the patient may choose if samples/images which are already collected but not analysed yet, can be analysed or shall be destroyed.

During the Dose-confirmation Phase, patients not evaluable for DLT will be replaced.

8.2.4 End of Study

After the End of Study Visit, all patients evaluable for efficacy will be followed for survival status according to local practice (a visit or a telephone call) every 12 weeks up to the end of study.

The study ends with the End of Study Visit of the last patient who discontinues the study treatment. For safety monitoring, all serious adverse events (SAEs) with a suspected causal relationship to the study treatment that occur after the End of Study must be recorded and notified to the Sponsor.

All biological samples except for safety blood samples collected along the study will be stored for a maximum of 10 years from the date of the Last Patient Last Visit. After 10 years, the samples will be destroyed.

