Note-1: Patients will be monitored at the site for occurrence of AE during cetuximab infusion and after the end of infusion for at least 1 hour.

Note-2: An ophthalmic visit shall be performed in case ocular disorders Grade ≥ 2 are assessed (the AE has to be followed until resolution to Grade 1). A dermatological visit shall be performed in case skin toxicity Grade ≥ 3 is assessed (the AE has to be followed until resolution to Grade 1). The frequency of ophthalmic and dermatological visits can be increased upon Investigator's judgement.

Note-3: For the whole study duration, unscheduled visits can be performed when further assessments are required as per the Investigator's judgement.

End of Study Visit (4 weeks after last administered dose of MEN1611):

- Physical examination including vital signs (i.e. BP, heart rate, respiratory rate, body temperature).
- Tumour assessment using RECIST v1.1 will be performed if the last assessment is older than 8 weeks.
- Assessment of ECOG PS.
- Smoking history and current smoking status.
- Blood samples for haematology, coagulation and chemistry.
- Sample for urinalysis.
- Recording of AEs and concomitant medications.
- Serum pregnancy test (if applicable).
- ctDNA levels and CTC enumeration assessments.

Note-1: All patients shall undergo the End of Study Visit at the scheduled day (at time frame of ± 7 days) or at the time of Study Withdrawal. Unscheduled assessment showing disease progression and leading to a patient's withdrawal can replace the End of Study Visit provided that all assessment/procedures scheduled for this visit are completed.

Note-2: Images collected at each tumour assessment time point have to be uploaded into a dedicated iMedidata Application according to the manual for retrospective central analysis.

Survival Follow-up:

After the End of Study Visit, all patients evaluable for efficacy will be followed for survival status according to local practice (a visit or a telephone call) every 12 weeks up to the End of Study.

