8.5.5.2 Secondary Endpoints

- Safety and tolerability:
 - Incidence, severity as per CTCAE v. 5.0 grading, seriousness and treatment-causality of TEAEs.
 - Frequency of clinically significant abnormalities in physical examination, safety laboratory tests, urinalysis, vital signs and 12-lead ECG.
- PK profile: MEN1611 plasma concentration-time data will be analysed using a population PK approach. A nonlinear mixed effects model will be used to determine population PK parameters and their associated variabilities (e.g. CL/F, V/F, Ka). Individual PK parameters (e.g. AUC, Cmax) will be estimated using a post hoc analysis.
- Disease Control Rate (DCR) defined as percentage of patients whose disease shrinks or remains stable over a certain time period. DCR is the sum of the complete, partial and stable disease rates according to local assessment.
- Duration of response defined as time from confirmation of a PR, CR or SD as locally assessed, until the disease has been shown to progress following treatment.
- PFS: Defined as the number of days between the first study treatment administration to the date of first documented disease progression as per local assessment, relapse or death from any cause. Responding patients and patients who are lost to follow-up are censored at their last tumour assessment date.
- OS: Defined as the number of days between the first study treatment administration and death from any cause.

For the baseline assessment, CT scan or MRI should be performed no more than 4 weeks before the start of study treatment. Follow-up assessment will be performed every 2 cycles during study treatment starting from Day 1 Cycle 3 (within a window of 7 days before the visit date) until objective disease progression as defined by RECIST v1.1 or at the End of Study Visit. Any other site at which a new disease is suspected should be appropriately imaged. If an unscheduled assessment is performed and the disease has not progressed, subsequent assessments should be performed at their scheduled visits.

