8.6.2 Monitoring and Recording of Adverse Events

At each visit the Investigator will assess any occurred subjective or objective AE, starting from the date of screening informed consent signature to the End of Study Visit.

The Investigator should manage as AE any laboratory test abnormality (newly occurring after the IMP administration or worsening of previously known abnormalities) considered as clinically significant as per Investigator’s judgement: i.e. values significantly above or under normal range or which require an intervention or diagnostic tests, or may result in the IMP discontinuation. The Investigator shall record on the respective eCRF-AE pages any AE, serious or non-serious, whether or not thought to be drug-related, observed in or reported by the patient (or relatives/delegates), specifying the judgement on the causal relationship with the study treatment. When the investigator confirms that all the collected information on any Individual Case Safety Report (ICSR; serious or not, related or not) has been entered in the eCRF, an email notification is automatically sent to the Sponsor.

AEs communicated by the patient or by the patient’s relatives or delegates through phone calls, letters or emails will also be recorded. In these cases, the Investigator will try to obtain medical confirmation and assessment of the occurred AE.

Any available information and diagnostic measure (laboratory and instrumental tests, procedures, etc.) shall also be recorded in the corresponding pages of the eCRF.

Progression of the disease under study will not be captured as an AE.

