9 STATISTICAL METHODS AND DETERMINATION OF SAMPLE SIZE

9.1 Determination of Sample Size

9.2 Analysis Populations

DLT population:

All patients receiving at least 80% of MEN1611 and 75% of cetuximab during Cycle 1 with a Safety Follow-up of 28 days after the first administration of the study treatment. Any patient who experiences a DLT will also be considered evaluable, regardless of the dose received.

Patients enrolled in the Dose-confirmation Phase, who are not DLT evaluable, will be replaced.

Safety population:

All patients receiving at least 1 dose of MEN1611.

Efficacy population:

All eligible patients who receive at least 2 complete treatment cycles and have at least 1 disease assessment are to be considered evaluable for efficacy.

PK population:

All patients receiving the study treatment and for whom a PK sample is obtained and analysed.

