7.3. Analysis populations

The following analysis populations will be considered in the statistical analysis:

- Safety population: all patients receiving at least 1 dose of MEN1611.
- DLT population: All patients receiving at least 80% of MEN1611 and 75% of cetuximab during Cycle 1 with a Safety Follow-up of 28 days after the first administration of the study treatment. Any patient who experiences a DLT will also be considered evaluable, regardless of the dose received. Patients enrolled in the Dose-confirmation Phase, who are not DLT evaluable, will be replaced. DLT Population is applicable only for the dose escalation phase patients, thus all Cohort Expansion patients will be not part of this population.
- Efficacy population: all eligible patients who receive at least 2 complete treatment cycles and have at least 1 disease assessment are to be considered evaluable for efficacy.
- PK population: All patients receiving MEN1611 and for whom a PK sample is obtained and analysed.

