12.1. Efficacy analysis

The following parameters will be summarized by cohort and overall (if appropriate) on the Efficacy population:

- Best Overall Response
- Disease Control Rate
- Objective Response Rate
- Duration of response (DoR)
- Progression Free survival (PFS);
- Overall Survival (OS).

ORR locally assessed is the primary endpoint of the Cohort Expansion Phase. All efficacy

endpoints related to tumour assessment will be evaluated considering both local (secondary endpoints) and central (exploratory endpoints) radiology assessments.

Best Overall Response (BOR) is derived as follows:

- If a subject has at least one overall response of CR, then BOR is CR;
- If a subject doesn't have any overall response of CR but has at least one overall response of PR, then BOR is PR;
- If a subject doesn't have any overall response of CR or PR but has at least one overall response of SD (or Non-CR / Non-PD) at least six weeks after the first intake of MEN1611, then BOR is SD (or Non CR / Non PD);
- If a subject doesn't have any overall response of CR, PR, SD (or Non-CR / Non-PD) after at least 6 weeks from the first intake of MEN1611, but has at least one overall response of PD, then BOR is PD;
- In all other cases, BOR is NE.

Objective Response Rate (ORR) is calculated as the sum of BOR rates of complete response (CR), partial response (PR).

Disease Control Rate (DCR) is calculated as the sum of BOR rates of complete response (CR), partial response (PR) and stable disease (SD).

Overall Survival (OS) is calculated as:

- In case of all-cause death:
OS = date of death - date of first study treatment administration + 1;
- In case of censored information not for drop-out:
OS = date of end of observation period (i.e. maximum between end of study and last follow up date) - date of first study treatment administration + 1;
- In case of censored information for drop-out:
OS = last available date in eCRF - date of first study treatment administration + 1.

Progression-free Survival (PFS) is calculated as:

- In case of death/disease progression:
PFS = date of death or date of first disease progression - date of first study treatment administration + 1
For subjects who experienced both death and progression disease, the date referred to the event that came first is considered.
- In case of censored information due to responding subjects or lost to follow-up:
PFS = date of censoring - date of first study treatment administration + 1

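### No survival follow-up is planned after the End of Study Visit for treated patients who are not evaluable for efficacy, so OS is selected on post-baseline events and an all-treated estimate would be biased upward

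*Protocol*

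**What the plan says.** **Survival follow-up.** Under Protocol 8.2.4, "all patients evaluable for efficacy will be followed for survival status" once they have had their End of Study Visit; contact is in person or by telephone, at 12-week intervals until the study closes. The same restriction appears in the synopsis (study duration and study procedures) and twice in 8.5.1. No other text provides survival contact for anyone else.

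**Who is evaluable.** Protocol 9.2 defines the Efficacy population as "All eligible patients who receive at least 2 complete treatment cycles and have at least 1 disease assessment". SAP 7.3 agrees.

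**The endpoint.** Protocol 8.5.5.2 reads "OS: Defined as the number of days between the first study treatment administration and death from any cause", with no evaluability condition. SAP 5.4.2 keeps that definition. In SAP 12.1 OS is among the endpoints governed by "The following parameters will be summarized by cohort and overall (if appropriate) on the Efficacy population".

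**The all-treated set.** SAP 7.3 has "Safety population: all patients receiving at least 1 dose of MEN1611".

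**Other routes by which a death could be recorded.** Adverse events are collected for all patients "starting from the date of screening informed consent signature to the End of Study Visit" (Protocol 8.6.2), and that visit falls four weeks after the last MEN1611 dose. Progression of the disease under study is not recorded as an adverse event. After the visit, Protocol 8.6.10 asks for active follow-up only of ongoing SAEs and non-serious events of special interest. It also asks for reporting of suspected treatment-related SAEs that the investigator learns of, and for follow-up of patients who stopped for safety reasons until the event resolves or the patient stabilises or recovers.

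**The concern.** The OS clock starts at first dose, but whether vital status is sought after the End of Study Visit depends on what happens in the following eight weeks or so. Patients who stop in Cycle 1 or 2 for toxicity, decline or progression shown before the Cycle 3 scan are treated and inside the endpoint definition, yet outside survival follow-up. They plausibly have the shortest survival.

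This is separate from the choice of analysis set. If the SAP were changed to analyse OS in all treated patients, those without a recorded death would be censored at or near their End of Study Visit, just when their prognosis is poor. That censoring is informative, and an edit to the SAP cannot supply the missing data.

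**Working it through.** The plan states no OS assumption to reproduce, and its sample-size sections are redacted. The check is therefore a comparison of rules followed by an illustration.

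**Step 1: which deaths can reach the database**

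| Death | Evaluable patient | Treated, not evaluable |
|---|---|---|
| Up to the End of Study Visit | Captured | Captured |
| Later, suspected related to treatment | Captured | Reported if the investigator learns of it |
| Later, from an SAE ongoing at the visit or the event that led to a safety stop | Captured | Followed to resolution, stabilisation or recovery |
| Later, disease-related or unrelated | Captured by 12-weekly contact | No planned route |

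The gap is the last cell.

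**Step 2: six-month OS**

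Inputs: 40 evaluable patients (synopsis target). Assumed: k = 4, 8 or 12 treated non-evaluable patients; exponential survival; median 262 days in evaluable patients (OS reported in Protocol 6.2 for a 33-patient cetuximab-oxaliplatin rechallenge study, borrowed for illustration); median m = 60, 90 or 120 days in non-evaluable patients.

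- Evaluable: S(183) = 0.5^(183/262) = 0.616.
- Non-evaluable: S(183) = 0.5^(183/m) = 0.121, 0.244 or 0.348.
- Full follow-up: [40 × 0.616 + k × 0.5^(183/m)] / (40 + k). For k = 12, m = 60: (24.65 + 1.45)/52 = 0.502. For k = 4, m = 120: (24.65 + 1.39)/44 = 0.592.
- Present rule: last dose uniform over weeks 0-8 (or at death if earlier); non-evaluable patients alive four weeks later are censored then. The Kaplan-Meier value at day 183 comes from a simulation of one million patients per scenario.

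| k | m (days) | Full follow-up | Censored at End of Study Visit | Gap (points) |
|---|---|---|---|---|
| 4 | 60 | 57.1% | 59.4% | 2.3 |
| 4 | 90 | 58.2% | 60.2% | 2.0 |
| 4 | 120 | 59.2% | 60.8% | 1.6 |
| 8 | 60 | 53.4% | 57.5% | 4.2 |
| 8 | 90 | 55.4% | 59.1% | 3.7 |
| 8 | 120 | 57.1% | 60.0% | 2.8 |
| 12 | 60 | 50.2% | 56.0% | 5.8 |
| 12 | 90 | 53.0% | 58.0% | 5.0 |
| 12 | 120 | 55.4% | 59.3% | 3.8 |

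Gaps are taken before rounding.

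**Step 3: separating the two effects**

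The evaluable-only figure is 61.6%. Its distance from full follow-up is 61.6 − 59.2 = 2.4 up to 61.6 − 50.2 = 11.4 points. That total mixes the analysis set with the follow-up rule. The follow-up rule alone accounts for 1.6 to 5.8 points; changing the analysis set would remove the rest.

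**Step 4: a second set of assumptions**

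Step 2 does not build in that evaluable patients survive about eight weeks. A second simulation does, with a 9.5-month median for them (the cetuximab arm of the KRAS wild-type comparison with supportive care in Protocol 6.2), 10%, 20% or 30% non-evaluable, and medians of 2 to 6 months for those patients.

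- Treated patients for 40 evaluable: 40/0.9 = 44.4, so 45; 40/0.8 = 50; 40/0.7 = 57.1, so 58. Without survival contact: 5, 10 or 18.
- All-treated median OS: 6.3 to 9.2 months with full follow-up, 7.9 to 9.3 months under the present rule. Scenario by scenario the overstatement is about 0.2 to 1.6 months.
- 54% to 81% of non-evaluable patients are alive at their End of Study Visit, so their later deaths mostly fall outside planned collection.

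**The case against.** Four points on the other side have force.

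- A reader might infer that deaths of non-evaluable patients are never recorded. The documents do not support that: every patient has an End of Study Visit, death is a listed reason for study withdrawal (Protocol 8.2.3.1), and Protocol 8.6.10 keeps open a route for treatment-related fatal events and for patients who stopped for safety reasons. This stands, and it narrows the gap to later disease-related or unrelated deaths.
- A reader might infer that all-treated OS could not be estimated. It could: SAP 5.4.2 and 12.1 give censoring rules, and a curve can be drawn. The fault is bias, not impossibility.
- A reader might count all early progressors as lost. The first scheduled scan falls within seven days before Cycle 3 Day 1, so a patient progressing there has had about two cycles and one assessment and may well qualify. Whether such a patient counts turns on how a complete second cycle is judged. Progression shown earlier is the clearer exclusion.
- OS is secondary, single-arm and descriptive, with no hypothesis test, and the primary ORR endpoint does not use survival contact. Collection also matches the planned analysis set, so the documents do not contradict themselves. This limits the stakes but leaves OS conditional on events after first dose.

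**Conclusion.** The concern holds in a limited form. Treated patients who are not evaluable for efficacy have no planned survival contact after the End of Study Visit, and their later disease-related or unrelated deaths are not planned to be collected. OS as planned is conditional on completing two cycles and having a scan. An all-treated curve from the same data would be biased upward.

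Under the stated assumptions the follow-up rule overstates six-month all-treated OS by about 1.5 to 6 points, or median OS by about 0.2 to 1.6 months. It would be wrong to attribute the whole 2 to 11 point distance between evaluable-only and all-treated OS to this rule, because part of it comes from the analysis set. The non-evaluable share, survival in that group, the dosing pattern and the transfer of outside survival figures are all assumed. The calculations show direction and plausible range, not a prediction. This is a worthwhile, inexpensive improvement and does not threaten the primary result.

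**What to change.** Three linked changes are needed; the first alone would leave the reported OS unchanged.

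1. In the synopsis, Protocol 8.2.4 and both places in 8.5.1, apply the 12-weekly survival contact to all patients who received at least one dose of MEN1611, in place of those evaluable for efficacy. This matches the defined Safety population.
2. For treated patients already off study, seek vital status and date of death retrospectively where consent allows, since a prospective change cannot reach them.
3. In SAP 12.1, report OS on the Safety population and keep the Efficacy-population OS as supportive.

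Cost: a protocol amendment, a SAP revision and a few telephone contacts per additional patient by the method already in use. No new visits or procedures are required.
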